ANNEX 3. ADDITIONAL INFORMATION

none

2. LIST OF ABBREVIATIONS

Term	Definition / description
AMI	Acute Myocardial Infarction
CEE	Central Eastern Europe
CHF	Congestive Heart Failure
CI	Confidence Interval
CKD	Chronic Kidney Disease
CTP	Clinical Trial Protocol
CVD	Cardiovascular Disease
DPP4	Dipeptidyl-peptidase 4
DPP4 i	Dipeptidyl-peptidase 4 inhibitor
FAS	Full Analysis Set
GLP1	Glucagon-like peptide 1
GLP1 a	Glucagon-like peptide 1 agonist
HCP	Health Care Provider
IHD	Ischemic Heart Disease
Max	Maximum
Min	Minimum
PAD	Peripheral Arterial Disease
PPS	Prescribed Patient Set
PV	Protocol Violation
SAP	Statistical Analysis Plan
SAS	Statistical Analysis System
SD	Standard deviation
SGLT2i	Sodium Glucose Transporter 2 inhibitor
T2D	Type 2 Diabetes

3. INTRODUCTION

As per ICH E9^[1], the purpose of this document is to provide a more technical and detailed elaboration of the principal features of the analysis described in the protocol, and to include detailed procedures for executing the statistical analysis of the primary and secondary variables and other data.

This TSAP assumes familiarity with the Observational plan, including Protocol Amendments. In particular, the TSAP is based on the planned analysis specification as written in Observational plan Section 9.7 “Data Analysis”. Therefore, TSAP readers may consult the Observational plan for more background information on the study, e.g., on study objectives, study design and population, treatments, definition of measurements and variables, planning of sample size, randomization.

SAS® Version 9.4 or higher will be used for all analyses.

4. CHANGES IN THE PLANNED ANALYSIS OF THE STUDY

Discontinuation rate, reason for discontinuation, duration of T2D therapy after one year (\pm 2 months) added as parameters collected on study index date 2

All adverse events and adverse drug reactions collected per study protocol will be included and summarized in the final study report.

[figure not shown]
5. OUTCOME(S)

5.1 PRIMARY OUTCOME(S)

The primary outcome of the presented study is to describe T2D patients' baseline characteristics when initiating either empagliflozin - or other SGLT2i, DPP4i or GLP-1 RA on top of current antidiabetic treatment by different HCP specialties in CEE countries.

5.2 SECONDARY OUTCOME(S)

- Burden of comorbidities (prevalence of CVD, CKD and CVD/CKD risk factors) in this T2D patient population at study index date 1
- Actual treatment use at study index date in patients with and without established CVD (Established CV disease defined as acute myocardial infarction (AMI), cardiology intervention, ischemic heart disease (IHD), congestive heart failure (CHF), peripheral arterial disease (PAD), or stroke)
- To describe the association of socioeconomic parameters with treatment decisions at study index date 1
- To assess the discontinuation rate, reasons for discontinuation and average duration of treatment for GLP-1 RA, DPP4i and SGLT2i after a follow up of approximately one year from the initial time point (= index date 2)

6. GENERAL ANALYSIS DEFINITIONS

6.1 EXPOSURE(S)

Exposure to SGLT2i, DPP4i or GLP-1 RA is defined as having received a first prescription of the respective treatment of interest between September and December 2018.

6.2 IMPORTANT PROTOCOL VIOLATIONS

Table 6.2: 1 defines the different categories of important protocol violations (PVs). The final column describes which PVs will be used to exclude subjects from the different patient analysis sets^[2].

Table 6.2: 1 Important protocol violations

Category/ Code	Description	Requirements	Excluded from
A	Entrance criteria not met		
A1.1	Inclusion criterion 2 (Female and male patients ≥ 18 years of age)	Not met as specified in the protocol	PPS
A1.2	Inclusion criterion 3 (Patients with T2D diagnosis)	Not met as specified in the protocol	PPS
A1.3	Inclusion criterion 4 (Patients who have been newly initiated (first ever use) with empagliflozin or other SGLT2i, DPP4i or GLP1a between September 2018 and December 2018 (study index date 1))	Not met as specified in the protocol	PPS
A1.4	Inclusion criterion 5 (Patients have been naïve to treatment with empagliflozin or other SGLT2i, DPP4i or GLP1a at study index date 1)	Not met as specified in the protocol	PPS
A2.1	Exclusion criterion 1 (Patients age < 18 years)	Met as specified in the protocol	PPS
A2.2	Exclusion criterion 2 (Patients with diagnosis of other types of diabetes than T2D)	Met as specified in the protocol	PPS
A2.3	Exclusion criterion 3 (Patients who do not provide written consent to the terms of the study)	Met as specified in the protocol	PPS
B	Exclusion criteria		
B1	Informed consent not available/not done (Inclusion criterion 1)	IC 01 not met as specified in the protocol or informed consent date	All

[figure not shown]
6.3 PATIENT SETS ANALYZED

Prescribed patient set (PPS): All patients fulfilling inclusion and exclusion criteria who have received a first prescription of a respective study medication.

Full Analysis set (FAS): All patients from PPS with documentation at index date 2. Patients included before the protocol amendment need an additional signed informed consent at index date 2.

Table 6.3: 1 Patient sets analyzed

Class of outcome	Patient set	
	PPS	FAS
Primary and secondary outcomes at index date 1	X	
Secondary outcomes at index date 2		X

6.5 POOLING OF CENTRES

Not applicable

6.6 HANDLING OF MISSING DATA AND OUTLIERS

No missing data will be imputed. If patients have missing values for an outcome, those patients will be excluded for that outcome's analysis.

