9.3 VARIABLES

The following parameters will be collected and assessed at study index date 1:

1. Patient demographics (age, gender, height, weight, BMI, ethnicity)
2. Time since diagnosis of Type 2 Diabetes
3. Clinical parameters relevant for T2D, CVD, CKD assessment (see below) as valid on study index date 1
4. Comorbidities like cardiovascular disease and related risk factors (see below) and Comorbidities like chronic kidney disease and related risk factors (see below) at study index date 1
5. T2D medication the treating physician newly prescribes at study index date 1
6. Concomitant T2D medications at study index date 1
7. Concomitant CVD and CKD medications at index date 1
8. Involvement of other HCPs in treatment decisions at study index date 1
9. Relevant socioeconomic parameters (see below) at index date 1

The following parameters will be collected and assessed at study index date 2 (= approximately one year ± 2 months after index date 1):

1. Status of T2D medication (continuation / discontinuation)
2. If discontinuation:
 - a. stop date of initial(index date 1) T2D medication (if available)
 - b. Reason for therapy discontinuation (see below)
 - c. Involvement of other HCPs in decision for therapy discontinuation

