 - sitagliptin
 - saxagliptin
 - vildagliptin
- GLP1a
 - dulaglutide
 - exenatide
 - liraglutide
 - semaglutide
 - lixisenatide
- Reasons for choosing the treatment rated as not relevant at all/ moderately relevant/ highly relevant
 - HbA1c lowering
 - Weight loss

- Cardiovascular risk reduction
- Favorable side effect profile
- Simple dosing / administration
- Guideline recommendation

[figure not shown]
6. Concomitant T2D medications (given as monotherapy or as fix combination with main T2D medication) at study index date 1
 - Metformin
 - Sulfonylurea
 - Acarbose
 - Pioglitazone
 - Insulin
 - others
7. Concomitant CVD and CKD medications at index date 1 (on class level only)
 - Antihypertensives ACEi or ARBs
 - Statins
 - Low dose aspirin
 - Beta blockers
 - Diuretics
8. Involvement of other HCPs in treatment decisions with regard to SGLT2i, DPP4i or GLP1a prescription at study index date 1 and with regard to discontinuation at index date 2 (yes/no; if yes, the medical specialty of the involved physician(s) should be specified)
9. Association of socioeconomic parameters with treatment decisions (such as employment status, family status, type of health insurance) at study index date 1
10. Status of T2D therapy approximately one year (\pm 2 months) after start
 - Stop date, if available
 - Reasons for discontinuation
 - Investigator's decision
 - Patient's request (difficulties in medication handling)
 - Patient's request (financial burden regarding co-payment)
 - Patient's request (other)
 - Lost to follow-up
 - Adverse event (in case of adverse reaction to empagliflozin or linagliptin or fatal adverse event, see [Section 11](#))
 - Death
 - Unknown
 - Other

Primary outcomes

- T2D patients' baseline characteristics when initiating either empagliflozin - or other SGLT2i, DPP4i or GLP1a on top of current antidiabetic treatment by different HCP specialties in CEE countries.

Secondary outcomes

- Burden of comorbidities (prevalence of CVD, CKD and CVD/CKD risk factors) in this T2D patient population at study index date 1
- Actual treatment use at study index date 1 in patients with and without established CVD (Established CV disease defined as acute myocardial infarction (AMI), cardiology intervention, ischemic heart disease (IHD), congestive heart failure (CHF), peripheral arterial disease (PAD), or stroke)
- To describe the association of socioeconomic parameters with treatment decisions at study index date 1

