9.10.2.2.1 Source documents

The relevant study data will be derived from the patient's medical record, which is maintained either paper-based or electronically depending on the routine at the respective study site. Data relevant for this study will be reviewed and entered into the study's eCRF by delegated site staff. Data entered in the eCRFs that are transcribed from source documents must be consistent with the source documents.

Source documents provide evidence for the existence of the patient and substantiate the integrity of the data collected.

For the eCRF, the following data must be derived from source documents:

1. Patient demographics (age, gender, height, weight, BMI, ethnicity)
2. Time since diagnosis of Type 2 Diabetes
3. Clinical parameters relevant for T2D, CVD, CKD assessment as valid on index date 1
4. Comorbidities like cardiovascular disease and related risk factors at index date 1
5. Comorbidities like chronic kidney disease and related risk factors at index date 1
6. T2D medication the treating physician newly prescribes at study index date 1
7. Reason(s) for treatment decision at index date 1
8. Concomitant T2D medications at study index date 1
9. Concomitant CVD and CKD medications at index date 1
10. Other HCPs involved in treatment decisions at study index date 1 and at index date 2
11. Relevant socioeconomic parameters
12. Status of T2D treatment (stop date and reason for discontinuation, if available) at index date 2

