7.4 SECONDARY OUTCOME(S)

All analysis will be descriptive and will be performed on PPS.

[figure not shown]
The prevalence of CVD and CKD will be displayed in frequency tables as well as the reasons for treatment choice, concomitant T2D medication and concomitant CVD/CKD medication. Furthermore other physicians involved in the treatment decision as well as the decision to discontinue the treatment will be given.

The "10 year risk for fatal CVD" will be calculated by applying the SCORE Risk Chart (European Society of Cardiology) taking into account patient's age, gender, systolic blood pressure, smoking status, and total cholesterol value at index date 1.

Moreover, the discontinuation rate and the reason for discontinuation will be displayed in frequency tables.

To assess the duration of T2D therapy after one year (\pm 2 months) the time to discontinuation will be analysed by Kaplan-Meier estimates and subgroups will be compared using log-rank test.

For comparison of subgroups, χ^2 -test or Fisher's exact test, if χ^2 -test is not valid, will be used. If the treatment decision depends on socioeconomic factors will be analysed using χ^2 -test or Fisher's exact test.

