10. HISTORY TABLE

Table 10: 1 History table

Version	Date (DD-MMM- YY)	Author	Sections changed	Brief description of change
Draft v0.1	30-APR-2019		None	This is the first Draft-Version of TSAP without any modification
Draft v0.2	24-JUN-2019		Headline, 3, 5, 5.1, 5.2, 5.3, 6.1, 6.3, 6.4, 6.6, 7.7	Adjusted wording to be conform with NIS status of the study
Draft v0.3	24-JUL-2019		6.3, [REDACTED]	Deleted obsolete information from 5.3 and 6.3 since these points were already part of primary and secondary outcomes. [REDACTED]
Final v1.0	13-Sep-2019		7.4, 8	Added reference for calculation of 10 year fatal CVD risk
Draft v1.1	10-Aug-2020		4,5,6,7	Adjusted to protocol amendment
Draft v1.2	23-OCT-2020		Titlepage, 5.1, 5.2, 6.1, 6.3, 6.4, 7, 7.4, 7.7	Adjusted wording according to reviewer comments/adaptations
Draft v 1.3	30-NOV-2020		7.4	Changed analysis method for duration of treatment to Kaplan-Meier assesment of time to discontinuation.
Final 2.0	10.DEC-2020		Page 1	Adapted Version and date. Applied all changes to finalize document.
Final 3.0	25.May-2021		6.3	Added FAS definition

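### The SAP's missing-data rule removes confirmed discontinuers without a stop date from the time-to-discontinuation analysis, so exclusion depends on the outcome

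*SAP*

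**What the plan says.** Protocol 9.3 collects treatment status at index date 2 (continued or discontinued) as a variable of its own. The date is conditional: Protocol 9.3.2 lists "Stop date, if available", and Protocol 9.10.2.2.1 lists "Status of T2D treatment (stop date and reason for discontinuation, if available) at index date 2". A patient can therefore be recorded as stopped with no date.

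SAP 6.6 rules out imputation and continues: "If patients have missing values for an outcome, those patients will be excluded for that outcome's analysis". SAP 7 repeats the exclusion.

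SAP 7.4 analyses objective 5 in two ways. For the rate, "the discontinuation rate and the reason for discontinuation will be displayed in frequency tables". For duration, "the time to discontinuation will be analysed by Kaplan-Meier estimates and subgroups will be compared using log-rank test". The SAP history table records the second method as a late change: "Changed analysis method for duration of treatment to Kaplan-Meier assesment of time to discontinuation".

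The visible SAP has no censoring rule, no rule for a stop without a date and no sensitivity analysis. Protocol 9.7.2 refers to the analysis plan for missing-data details.

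**The concern.** An event time needs a date; a status does not. Under the exclusion rule, the only patients who can leave the time-to-discontinuation analysis for want of a stop date are those who had the event. Continuers have no stop date to lose. Selection into the curve therefore depends on the outcome being estimated.

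The frequency table needs status only and keeps the undated stops. Table and curve would then describe different patients in the same report. The subgroup log-rank test rests on the reduced set as well, so subgroups with different undated shares could appear to differ in persistence when they do not.

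**Working it through.** **Inputs.** From the documents: status is recorded separately from the stop date (Protocol 9.3); assessment is at 12 ± 2 months, that is 10 to 14 months (Protocol 9.1, 9.3); about 4000 patients, with targets of at least 1000 each on SGLT2i and DPP4i and 500 on GLP1a (Protocol 9.5). The documents give neither a discontinuation rate nor an undated share, so there is no planned figure to reproduce. Both are assumed below: p is the true 12-month proportion stopped, and q is the share of stops without a date.

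**Step 1: undated stops unrelated to timing.** Removing a fraction q of the stoppers leaves p(1−q) events among 1−pq patients, so the curve reads p(1−q)/(1−pq). With 4000 patients and p = q = 20%, the table gives 800/4000 = 20.0% and the curve gives (800−160)/(4000−160) = 640/3840 = 16.7%.

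| True p | q = 2% | 5% | 10% | 20% | 30% |
|---|---|---|---|---|---|
| 10% | 9.8 | 9.5 | 9.1 | 8.2 | 7.2 |
| 20% | 19.7 | 19.2 | 18.4 | 16.7 | 14.9 |
| 30% | 29.6 | 28.9 | 27.8 | 25.5 | 23.1 |

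A simulation (400,000 patients, exponential stop times, censoring uniform over 10 to 14 months) gives 20.0% with all dates present and 16.7% at q = 20%. The gap therefore comes from the exclusion and not from the assessment window.

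**Step 2: undated stops related to timing.** Suppose only stops after month 12 lack a date. In the same model these are 3.7% of stops, or 0.037 × 20% = 0.74% of patients. All were event-free at month 12, so removing them shrinks the denominator only: 0.20/(1−0.0074) = 20.15%. The 12-month estimate rises slightly, and the curve is too low only beyond month 12.

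**Step 3: duration.** With exponential times and 20% stopped at 12 months, λ = −ln(0.8)/12 = 0.0186 per month, and the restricted mean to 12 months is 0.2/λ = 10.76 months. Stoppers average (10.755 − 0.8×12)/0.2 = 5.78 months. After exclusion the mean is [9.6 + 0.2(1−q)×5.78]/(1−0.2q), which is 10.81, 10.86 and 10.96 months at q = 5, 10 and 20%. The rise is about 1.5, 3 and 6 days.

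**Step 4: log-rank test.** Identical true persistence (20% stopped at 12 months), assessment uniform over 10 to 14 months, nominal 5% level, 10,000 replicates:

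| Undated shares in the two groups | Group sizes | Rejection, undated stops dropped | Rejection, midpoint dates |
|---|---|---|---|
| 10% v 10% | 1000 v 1000 | 5.2% | 5.2% |
| 5% v 10% | 1000 v 1000 | 7.1% | 4.9% |
| 10% v 20% | 1000 v 1000 | 16.8% | 5.1% |
| 5% v 10% | 1000 v 500 | 6.4% | 5.0% |
| 10% v 20% | 1000 v 500 | 12.4% | 5.1% |

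Equal shares do no harm. Small differences matter little: with 1000 per group and 4000 replicates, rejection is 5.3% at 1% v 2% and 6.7% at 2% v 5%.

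**Step 5: the informal alternative.** Treating an undated stop as still on treatment and censoring it at index date 2 does not help. At p = q = 20% the simulated curve reads 16.0%, lower than with exclusion.

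**The case against.** The strongest reply is that the consequence is slight. SAP 7.4 reports the discontinuation rate by frequency table, which keeps every recorded stop, and uses the curve for duration, where the bias is a matter of days. Protocol 9.7.2 expects little missing data, Protocol 9.8 plans completeness checks at entry, and all testing is exploratory. This stands as to size. It does not remove the mechanism: no undated share is given, and the stop date is expressly optional. It arrived with Amendment 1, whose change list does not name Protocol 9.7.2, so it is open whether the expectation of few missing values covers it.

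Three stronger readings are tempting, and the documents do not support them.

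- A reader might infer that the curve must always be too low. Step 2 shows that the direction at month 12 depends on which stops are undated.
- A reader might infer that the report will carry two conflicting one-year rates. The SAP does not list a 12-month Kaplan-Meier percentage as an output. The table also gives status at index date 2 and not at month 12: with every date present and a true 20% at 12 months, it would read about 1 − 0.8^(10.5/12) = 17.7% if assessments cluster at 10 to 11 months, and 1 − 0.8^(13.5/12) = 22.2% at 13 to 14 months. A gap between table and curve would not by itself prove this bias.
- A reader might infer that the log-rank test is invalid. That needs undated shares that differ between subgroups, which the documents neither show nor exclude.

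Two cautions limit confidence. Censoring of continuers is inferred from ordinary practice, and SAP headings 6.4 and 7.5 are blank in the available copy, so their content cannot be checked. The history table is weak evidence either way: it names only 7.4 for the Kaplan-Meier change, but section 6 had been revised for the amendment a few months before.

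**Conclusion.** The point holds as a biasing rule and not merely as missing detail: on the visible text, SAP 6.6 and 7 take confirmed discontinuers out of the time-to-discontinuation analysis because of a field the protocol makes optional. If lacking a date is unrelated to timing, a true 20% at 12 months reads 19.2 to 16.7% at undated shares of 5 to 20%; if only late stops are undated, it may read about 20.2%. With no undated stops there is no bias.

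Only objective 5 is affected, and within it only the curve and the log-rank comparison. The primary outcome and the frequency table are untouched by this rule. Severity is minor to moderate and confidence moderate.

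The protocol also lists "Lost to follow-up", death and unknown among the reasons for discontinuation. Which of these count as a stop needs its own clarification; it does not arise from SAP 6.6 and adds no weight here.

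**What to change.** Amend SAP 6.6 and 7.4, with a cross-reference where SAP 7 repeats the rule:

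1. Exempt time to discontinuation from the exclusion rule. Keep confirmed discontinuers without a stop date as events, either interval-censored between index date 1 and the index-date-2 assessment or dated by one pre-specified rule such as the midpoint.
2. State the censoring date for continuers and take it from the same source as the upper bound for undated stops: the assessment date if the eCRF holds it, otherwise one nominal date within 12 ± 2 months for both. Consistency matters. For a true 20%, a 14-month bound for undated stops combined with actual censoring dates for continuers still reads 17.3% at 20% undated, whereas one nominal date for both reads 19.2 to 19.5%.
3. Report the number of undated stops by subgroup, with a dated-only analysis as sensitivity.

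In simulation, midpoint dating reads 20.0% for a true 20% at undated shares of 5 to 30%, and interval censoring to the assessment date reads 19.7 to 19.9%.

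The cost is SAP wording and a little programming, with no new data. The remaining assumption is that lacking a date is unrelated to when the patient stopped. At 30% undated and 1000 patients, the simulated standard error of the 12-month rate is 1.3 points against 1.1.

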6.7 BASELINE, TIME WINDOWS AND CALCULATED VISITS

At Index Date 1 the patients initially prescribed with T2D medication (empagliflozin or other SGLT2i, DPP4i or GLP-1 RA). At Index Date 2 (after 1 year (\pm 2 months) the discontinuation rate, reason for discontinuation and average duration of T2D treatment will be assessed.

7. PLANNED ANALYSES

All patients who have received a first prescription of respective study medication will be included in the analysis; this is the prescribed patient set. All analyses at index date 1 will be performed on the prescribed patient set and analyses at index date 2 will be performed on the full analysis set. If patients have missing values for an outcome, those patients will be excluded for that outcome's analysis.

The assessment will be carried out using SAS® software. The statistical characteristics presented in the end-of-text tables will be N / mean / SD / min / median / max for continuous variables. Tabulations of relative and absolute frequencies will be presented for categorical variables. Incidence rates and 95% CI will be given when appropriate. Subgroup analyses e.g. according to medication (i.e. empagliflozin or SGTL2i or DPP4i or GLP-1 RA), country and physician specialty are planned, as well as per history of CV disease. Descriptive analyses will be supplemented using χ^2 -test or Fisher's exact test for categorical variables and Wilcoxon-Mann-Whitney test for continuous variables. The analyses are purely explorative, hence no correction for multiple testing is needed.

The analyses will relate to the following data as recorded in the eCRF:

1. Patient demographics (age, gender, height, weight, BMI, ethnicity)
2. Time since diagnosis of Type 2 Diabetes
3. Clinical parameters relevant for T2D, CVD, CKD assessment as valid on index date 1
4. Presence of cardiovascular disease and related risk factors at index date 1
5. Presence of chronic kidney disease and related risk factors at index date 1
6. T2D medication the treating physician newly prescribes at study index date 1
7. Reason(s) for treatment decision at index date 1
8. Concomitant T2D medications at study index date 1
9. Concomitant CVD and CKD medications at index date 1
10. Other HCPs involved in treatment decisions at study index date 1 and at index date 2
11. Relevant socioeconomic parameters
12. Discontinuation rate, reason for discontinuation, duration of T2D therapy after one year (± 2 months)

All adverse events and adverse drug reactions collected per study protocol will be included and summarized in the final study report.

For the main analysis data from research question 1 to 5 will be evaluated in a descriptive manner for the total number of prescribed patients enrolled in the study.

To allow a country specific interpretation of the results, data from research question 1 to 5 will be evaluated in a descriptive manner for the total number of prescribed patients per country enrolled in the study.

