8.2 STUDY OBJECTIVES

The objective of the study is

1. To describe and compare T2D patients' baseline characteristics when initiating either empagliflozin - or other SGLT2i, DPP4i or GLP1a on top of current antidiabetic treatment by different HCP specialties in CEE countries
2. To describe the prevalence of comorbidities (prevalence of CVD, CKD) in this T2D patient population at index date 1
3. To describe and compare the actual treatment uses at index date 1 in patients with and without established CVD

Established CV disease defined as acute myocardial infarction (AMI), cardiology intervention, ischemic heart disease (IHD), congestive heart failure (CHF), peripheral arterial disease (PAD), or stroke.

4. To describe the association of socioeconomic parameters with treatment decisions at index date 1
5. To assess the discontinuation rate, reasons for discontinuation and average duration of treatment for GLP1a, DPP4i and SGLT2i after a follow up of approximately one year from the initial timepoint (= index date 2)

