9.5 STUDY SIZE

No formal sample size calculation is provided for this study. This NIS has been designed to describe, in a real-world setting, usage patterns and outcomes associated with empagliflozin or other SGLT2i or DPP4i or GLP1a in the clinical routine practice. The sample size of approximately 4000 patients is driven by the need to enroll an adequate number of patients to address the mentioned objectives, also across various subgroups, such as physician or country specific analyses. It is aspired to document at least 500 patients in the GLP1a and at least 1000 patients each in the SGLT2i and DPP4i subgroups. However, no formal limitations will be applied for recruitment of patients to subgroups with regard to medication of interest.

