7.3 PRIMARY OUTCOME

For the primary outcome, the baseline characteristics will be analysed in a descriptive manner. Frequencies and 95% CI will be given when appropriate.

In addition the baseline characteristics will be compared by medication, physician speciality and country using χ^2 -Test or Fisher's exact test, if χ^2 -Test is not valid, for categorical variables and Wilcoxon-Mann-Whitney test for continuous variables.

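### The primary objective promises a comparison of baseline characteristics, but no between-group difference with a confidence interval is planned; the only comparative statistic is an uncorrected p-value

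*SAP*

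**What the plan says.** Protocol 8.2 gives the first objective as "To describe and compare T2D patients' baseline characteristics when initiating either empagliflozin - or other SGLT2i, DPP4i or GLP1a on top of current antidiabetic treatment", by specialty, in the participating countries. SAP 5.1 keeps only the first verb: "The primary outcome of the presented study is to describe T2D patients' baseline characteristics". SAP 7.3 nevertheless plans the comparison: "In addition the baseline characteristics will be compared by medication, physician speciality and country using" chi-square or Fisher tests for categorical variables and Wilcoxon-Mann-Whitney tests for continuous ones.

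Around those tests the SAP plans group-level summaries. For continuous variables, "The statistical characteristics presented in the end-of-text tables will be N / mean / SD / min / median / max for continuous variables"; categorical variables get counts and percentages. SAP 7.3 adds "Frequencies and 95% CI will be given when appropriate". SAP 7.4 uses chi-square or Fisher tests alone to judge whether treatment choice depends on socioeconomic factors.

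On multiplicity, SAP 7 states: "The analyses are purely explorative, hence no correction for multiple testing is needed". On size, Protocol 9.5 gives no formal calculation, plans about 4000 patients, hopes for "at least 500 patients in the GLP1a and at least 1000 patients each in the SGLT2i and DPP4i subgroups", and sets no limit on recruitment to any medication group. In the ENCePP checklist (Protocol Annex 2), the items on measures of association (3.4) and on study size or precision (10.2) are both marked not applicable.

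**The concern.** A comparison should say how far apart two groups are and how precisely that is known. In the visible text of SAP 7, 7.3 and 7.4, no difference, ratio or shift between groups is specified for the baseline or socioeconomic comparisons. The 95% CIs attach to frequencies, not to differences between them. No significance level is stated, no size of difference is named as relevant, and there is no rule for reading the p-values.

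Waiving multiplicity correction is reasonable in exploratory work as long as p-values are not what marks a difference as found. Here the plan offers no other comparative quantity. The risk is that the report sorts characteristics into different and not different by p<0.05. That sorting would depend partly on how many patients each group recruited, and it would include some chance results with no interval beside them to show their size.

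**Working it through.** The documents state no alpha, power, effect size or number of tests, so there is no figure of the plan's own to reproduce. A two-sided 5% level is assumed throughout.

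**1. Group size and the smallest gap that reaches p<0.05**

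Inputs: the group targets in Protocol 9.5, and 34%, the Swedish CVD prevalence cited in Protocol 8.1, used only as an illustration.

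Smallest gap = 1.96 × √[0.34 × 0.66 × (1/n₁ + 1/n₂)], with 0.34 × 0.66 = 0.2244. This is also the approximate half-width of a 95% CI for the difference.

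| Groups | Source of sizes | Gap (points) |
|---|---|---|
| 1000 vs 1000 | SGLT2i and DPP4i minimum targets | 1.96 × √(0.2244 × 0.002) = 4.2 |
| 500 vs 1000 | GLP1a target vs either | 1.96 × √(0.2244 × 0.003) = 5.1 |
| 500 vs 500 | assumed split of 1000 SGLT2i into empagliflozin and other | 5.9 |
| 200 vs 800 | assumed uneven split of the same 1000 | 7.3 |
| 571 vs 571 | two countries, assuming 4000/7 each | 5.5 |
| 100 vs 571 | assumed small country vs an average one | 10.1 |

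Empagliflozin versus other SGLT2i has no size target of its own.

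Take an observed gap of 5.0 points. At 1000 vs 1000 the CI is 5.0 ± 4.2, about 0.8 to 9.2, and p<0.05. At 500 vs 1000 it is 5.0 ± 5.1, about −0.1 to 10.1, and p>0.05. The two results are nearly the same, but a p-value reading would call one a difference and the other not.

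For a continuous variable, the power to detect a true difference of 0.2 SD is Φ(0.2/√(1/n₁ + 1/n₂) − 1.96). This is 0.99 at 1000 vs 1000, 0.95 at 500 vs 1000, and 0.45 at 100 vs 571.

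**2. Number of tests**

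Items are counted from Protocol 9.3.2 and multiplied by the three factors in SAP 7.3.

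- Narrow list: 6 demographic items, 1 for diabetes duration and 11 clinical values = 18 items; 18 × 3 = 54 tests. Counting whether an echocardiogram was done as a separate item gives 19 × 3 = 57.
- Widest list: 19 + 7 comorbidity items + 8 risk factors + 6 concomitant T2D drugs + 5 CVD/CKD drug classes + 6 reasons for choice + 1 other-HCP item + 3 socioeconomic items = 55; 55 × 3 = 165 tests. Much of this list sits under secondary outcomes in the SAP.
- Wilcoxon-Mann-Whitney is a two-sample test, but the factors have 4 medication, 7 country and 3 specialty levels. Pairwise use means 6 + 21 + 3 = 30 pairs. For the 19-item list, 16 continuous items × 30 + 3 categorical items × 3 = 489 tests.

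Expected false positives if nothing differs (tests × 0.05; independence is not needed): 54 gives 2.7, 165 gives 8.25, 489 gives 24.5. The SAP does not say whether tests are overall or pairwise, so each count is an assumption.

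**3. Can readers recover the estimates?**

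Partly. Differences in percentages or means follow from the group tables, and approximate CIs from N and SD. A Hodges-Lehmann interval, the natural companion to the Wilcoxon test, cannot be rebuilt from N, mean, SD, minimum, median and maximum.

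**The case against.** The plan is openly descriptive. SAP 7.1 limits the baseline section to descriptive statistics, SAP 7 says the tests only supplement the tables, and the checklist (2.1.4) marks hypotheses as not applicable. Group means and percentages will be tabulated by medication, country and specialty, so crude differences can be read off. Leaving out multiplicity correction in a declared exploratory study is a defensible choice. All of this stands, and the request is therefore for better reporting, not for a correction procedure.

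It is also fair that the two main class contrasts differ little: 5.1 − 4.2 = 0.9 points at the minimum targets. The dependence on size becomes marked only in smaller groups, whose sizes are assumed here.

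A reader might infer several stronger things that the documents do not support:

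- That results will be reported only as p-values. They will not; group summaries accompany them.
- That one definite number of tests exists. The count depends on the variable list and on whether tests are overall or pairwise.
- That any list of differences would be only an artefact of group size and chance. Real differences between drug classes, countries and specialties are plausible; size and chance contribute, but need not explain the list.
- That medications will be tested against each other inside each country. SAP 7 says "To allow a country specific interpretation of the results, data from research question 1 to 5 will be evaluated" descriptively for each country, and SAP 7.3 compares by country. Within-country testing is not excluded, but it is not clearly planned.

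**Conclusion.** The point holds as a gap in what will be estimated. Objective 1 promises a comparison, and the visible SAP plans no between-group effect estimate with a CI for it, nor for the socioeconomic association. The Kaplan-Meier analysis of discontinuation in SAP 7.4 is a separate matter.

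The sizes are illustrative: thresholds of about 4.2 to 5.1 points at the stated minimum targets, larger for smaller groups, and about 3 to 8 expected false positives with one overall test per factor, or about 24 or more if Wilcoxon tests are pairwise. They rest on an assumed 5% level, a 34% reference prevalence, the targets taken as final sizes, and the item counts above. The descriptive tables remain valid without the change. What is missing is a planned statement of how large the differences are and how precisely they are known.

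**What to change.** Amend SAP 7.3 and 7.4 as follows:

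- Name the contrasts: for medication, for example empagliflozin versus other SGLT2i, versus DPP4i and versus GLP1a; for specialty, the pairs of interest.
- For each, report the difference in percentage points (categorical) or the mean or Hodges-Lehmann difference (continuous), with its 95% CI. A standardised difference may be added as description.
- For the socioeconomic question, report differences in the proportion receiving each medication group, with 95% CIs.
- Base the report's text on these estimates, and label all p-values nominal.
- State whether tests are overall or pairwise, and how many there are.

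No fixed cut-off on the standardised difference should replace p<0.05. With no true difference, an absolute value of 0.1 is exceeded by chance about 7% of the time at 500 vs 1000 (0.1/√0.003 = 1.83 standard errors), and more often in smaller groups.

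No new data are needed. The cost is SAP wording, extra table columns, longer tables and fewer statements of significance.
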